17.8.6 Nicotine, NNN and NNK extraction comparison (Part 1 and Part 3)

The difference in contents between unused and used pouches/loose snus portions will be used to calculate the *in vivo* extraction. The calculated extracted amounts of nicotine, NNK, and NNN per pouch/loose snus will be averaged per subject and multiplied with the consumption (number of pouches/loose snus used per day on average) reported in the eDiary over the 14 days *ad libitum* usage period, to receive the daily exposure.

Daily exposure to nicotine, NNK, and NNN will be summarized descriptively and analyzed using the same model and principles as outlined under Section 17.8.5.

Average extracted amounts (mg/unit) and fractions (%) of nicotine, NNK, and NNN will also be summarized descriptively.

Additionally, the subgroup "loose snus users" will be analyzed and presented separately.

17.8.7 Nicotine, NNN and NNK extraction correlation to biomarkers of exposure (Part 1 and Part 3)

Daily exposure to nicotine, NNK, and NNN will be calculated as described under Section 17.8.6. The intake will be correlated with urine concentrations of BoE (nicotine, cotinine, NNN, NNAL, and anabasine) for dose-relationship investigations using linear regression with BoE levels as the dependent variable and daily exposure to nicotine, NNK, and NNN as a continuous explanatory variable in separate models. Subject will be included in the models as a random effect.

CONFIDENTIAL 71(76)

In total the following models will be developed (refer to Table 17.8-1):

Table 17.8-1 Correlation analysis models

Model number:	Dependent variable:	Explanatory variable:
Model 1	Nicotine (Nic) in urine	Daily exposure to nicotine
Model 2	Cotinine (Cot) in urine	Daily exposure to nicotine
Model 3	4-(Methylnitrosamino) -1-(3-pyridyl) -1-butanol (NNAL) in urine	Daily exposure to nicotine
Model 4	N -nitrosonornicotine (NNN) in urine	Daily exposure to nicotine
Model 5	Anabasine in urine	Daily exposure to nicotine
Model 6	3'-trans-hydroxycotinine (OH-Cot) in urine	Daily exposure to nicotine
Model 7	Nicotine equivalents in urine	Daily exposure to nicotine
Model 8	4-(Methylnitrosamino) -1-(3-pyridyl) -1-butanol (NNAL) in urine	Daily exposure to NNK
Model 9	N -nitrosonornicotine (NNN) in urine	Daily exposure to NNN

To all of the models above, the product (including subject's own brand, NP 6 mg, NP 11 mg, and NP 16.6 mg) will be fitted as dummy variables. Additionally, the interaction effect between daily exposure to nicotine/NNK/NNN and the product will be considered, resulting in different regression slopes for each product. The regression results will be presented graphically, along with model fit statistics and p-values from hypothesis tests, highlighting differences between products in terms of daily exposure to nicotine/NNK/NNN and the BoE correlation. Depending on model diagnostics, the analysis approach may be updated – for instance, grouping NP products or using scatter plots to visualize relationships without inferential statistics.

Additionally, the subgroup "loose snus users" will be analyzed and presented separately.

CONFIDENTIAL 72(76)

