6.3.3 Risk/benefit conclusion

The long-term health risks of NPs are not known. Since they contain fewer harmful substances than tobacco-based snus, as they do not contain tobacco, the extensive research available for tobacco-based snus can be used to estimate the long-term health risks of NPs, provided that the nicotine exposure from NPs is not higher than from tobacco-based snus.

Nicotine exposure is primarily dependent on the nicotine content and consumers' usage patterns. The nicotine content in tobacco-based snus and NPs varies greatly and differs between markets (1.5-150 mg per pouch). In Sweden, SIS has established a limit of 20 mg per pouch. NPs with a nicotine content below this threshold are deemed safe for consumer use.

The overarching aim of the study is to achieve a comprehensive understanding of how nicotine content affects actual nicotine exposure, addiction potential, and whether the long-term health risks of NPs can be estimated based on the epidemiological studies available for tobacco-based snus. As the use of NPs has increased significantly in recent years and the products vary greatly in nicotine content, it is important to try to estimate how this affects, for example, long-term cardiovascular health.

In this study, NPs with 3 different nicotine contents will be used, all of which are within the recommended limits and reflect the products commonly used by consumers in Sweden. The

CONFIDENTIAL 24(76)

results of the study can guide the establishment of recommendations and regulations regarding appropriate nicotine limits to restrict the nicotine content of NPs.

In Part 3 of the study, there is a potential risk that some subjects may be exposed to higher levels of nicotine than usual during the 14-day period. However, the nicotine contents in the NP products are below the limits set by SIS and BfR, indicating that the associated risks are expected to be low. Additionally, many consumers already use snus or NP products with high nicotine content, and the study products are similar to those available on the market. Therefore, while there is a risk of increased nicotine exposure, the overall benefit of the study is supported by the low expected risk and the relevance of the study products to existing consumer habits.

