5.	To compare urine concentrations and amounts of BoE (nicotine and its metabolites, NNN, NNAL, and anabasine) before and after complete substitution of own brand snus product with a moist NP product for 14 days.	5.	Difference in creatinine-normalized urine concentrations and amounts of BoE (nicotine and its metabolites, NNN, NNAL, and anabasine) before and after complete substitution of own brand snus product with a moist NP product for 14 days.	(Section 11.6.1.5)	See Section 17.8.5.	
6.	To compare the extracted amounts and fractions of nicotine, NNN, and NNK from used and collected own brand snus pouches/portions and used moist NPs.	6.	Difference in the extracted amounts (mg/unit) and fractions (%) of nicotine, NNN, and NNK from used and collected pouches/portions during each of the two 14-day ad libitum usage periods of either own brand snus product usage or complete substitution with a moist NP product.	(Section 11.6.1.2)	See Section 17.8.6.	
7.	To correlate the extracted amounts of nicotine, NNN, and NNK, multiplied by the number of pouches/portions used per day on average, with urine concentrations of BoE.	7.	The correlation between the extracted amounts (mg/unit) of nicotine, NNN, and NNK, multiplied by the number of pouches/portions used per day on average, and the creatinine-normalized urine concentrations of BoE before and after complete substitution of the own brand snus product with a moist NP product for 14 days.	(Section 11.6.1.2 and 11.6.1.5)	See Section 17.8.7.	

1. Loose snus users will be analyzed as a subgroup for all exploratory endpoints.

CONFIDENTIAL 28(76)

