11.6.1.2 Nicotine and tobacco-specific nitrosamines extraction related to exploratory endpoints

Nicotine extraction related to exploratory endpoint 2 is part of the procedure described in Section 11.5.2 above.

For Part 1 and 3, nicotine extraction (related to exploratory endpoints 6 and 7) will be calculated from analysis of used pouches/loose snus collected by the subject during *ad libitum* use of the subject's own brand Swedish snus (Part 1) and the selected NP product (Part 3).

Used pouches/loose snus will be shipped frozen to Swedish Match for chemical analysis of the extracted amount of nicotine, NNK, and NNN. The Sponsor will purchase the applicable products used by the subjects in Part 1 for chemical characterization of the unused pouches/loose snus at Swedish Match. For pouched products, the calculation of the extracted amount and fraction of nicotine, NNK, and NNN will involve subtracting the average of the pouches used by the subjects from the average of 10 unused pouches. For loose snus users, the calculation is based on a single unused reference portion. The weight of this reference portion is identical to the portion that each user prepares themselves during Part 2.

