17.6 Analysis of primary endpoint

17.6.1 Comparison of the NP 11 mg and Swedish snus comparator (AUC_{0-inf})

The primary endpoint of this study is to compare nicotine exposure, as measured by baseline-adjusted AUC_{0-inf} based on nicotine plasma concentrations, between the NP 11 mg product and the comparator product, Swedish snus pouch 18 mg. The goal is to demonstrate that the upper bound of the 95 % confidence interval of the ratio for nicotine exposure of the moist NP 11 mg product and the comparator Swedish snus product is at or below 1.25.

AUC_{0-inf} will be calculated as described in Section 17.4 above.

The comparison of AUC_{0-inf} between the NP 11 mg and the comparator Swedish snus pouch 18 mg will be assessed using the following null (H_0) and alternative (H_1) hypotheses:

$$H_0: \frac{\mu_T}{\mu_R} > 1.25$$

$$H_1: \frac{\mu_T}{\mu_R} \le 1.25$$

where μ_T is the least-squares geometric mean of $AUC_{0\text{-inf}}$ for the NP 11 mg and where μ_R is the least-squares geometric mean of $AUC_{0\text{-inf}}$ for the comparator Swedish snus pouch 18 mg.

In the analysis, a mixed model will be used with the natural log of $AUC_{0\text{-inf}}$ as the dependent variable, treatment as a fixed effect and subject as a random effect. The improved Kenward-Roger's approximation for degrees of freedom [23] will be used. The estimated least-squares means difference between the NP 11 mg and the comparator Swedish snus pouch 18 mg will be back-transformed into the original scale to present the ratio of geometric least square means as well as the corresponding 95 % confidence interval. If the upper bound of the interval of this ratio is at or below 1.25, the null hypothesis will be rejected, and it will be concluded that the NP 11 mg product does not result in substantially higher nicotine exposure compared to the comparator product.

CONFIDENTIAL 68(76)

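### Section 17.8.6 puts Part 3 NNN and NNK exposure, a difference likely to be near zero for tobacco-free pouches, through a log-ratio model that cannot use zero or negative values

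*Protocol*

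**What the plan says.** **Derived variable.** Protocol section 11.6.1.2 obtains the extracted amount for pouched products by "subtracting the average of the pouches used by the subjects from the average of 10 unused pouches". Section 17.8.6 repeats the subtraction and has the result "averaged per subject and multiplied with the consumption" reported in the eDiary, which gives daily exposure. Neither section bounds the result at zero.

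**Model.** Section 17.8.6 then states: "Daily exposure to nicotine, NNK, and NNN will be summarized descriptively and analyzed using the same model and principles as outlined under Section 17.8.5". Section 17.8.5 takes its model from the primary analysis in 17.6.1, where "a mixed model will be used with the natural log of" the outcome as dependent variable, and adds an equivalence rule: the 90% confidence interval for the geometric ratio must lie within 0.8 to 1.25.

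**Product.** In Part 3 every subject uses a nicotine pouch. Section 6.3.3 says these contain fewer harmful substances than snus, "as they do not contain tobacco". Section 6.3.1 describes their nicotine as pharmaceutical grade. The heading of 11.6.1.2 calls NNN and NNK tobacco-specific nitrosamines.

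**Handling rules.** Section 17.1.1 generally excludes imputation and leaves missing, unused and spurious data to the SAP. The only rule for values below the quantification limit, in 17.7.2, concerns plasma nicotine relative to Cmax.

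**The concern.** A log-ratio model suits an outcome that is always positive. Extracted nicotine should be, and so should NNN and NNK extracted from own brand snus. For NNN and NNK from a tobacco-free pouch, the plan takes the log of a difference between two quantities that its own description places at or near zero. Multiplying by units per day keeps the sign, so a zero or negative difference remains one.

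A mixed model on the log scale omits such records, and the omission depends on the outcome: low values go and high values stay. At stake is the Part 3 versus Part 1 comparison of NNN and NNK intake, part of exploratory endpoint 6: "Difference in the extracted amounts (mg/unit) and fractions (%) of nicotine, NNN, and NNK from used and collected pouches/portions".

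**Working it through.** The plan gives no figure for this analysis. The only count to borrow is the Part 2 target of 45 evaluable subjects in 17.2, used here just to turn shares into numbers. That target reproduces to within one subject: σ² = ln(1 + 0.33²), σ = 0.3215; n = 2 × 0.3215² × (1.960 + 1.282)² / (ln 1.25)² = 43.6, so 44 by the normal approximation against 45 stated; 45/0.85 = 52.9, so 53.

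**Inputs from the protocol**
- 10 unused pouches in the reference mean (11.6.1.2).
- 8 used pouches per week, so 16 per 14-day period (8.1.3).
- Model chain 17.8.6 → 17.8.5 → 17.6.1, natural log.

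**Inputs assumed**, because the protocol gives no NNN/NNK content, quantification limit or assay noise for the pouches
- Trace content scaled to 1; true extracted fraction f; per-pouch SD s from 0.3 to 1.0; normal noise; an independent reference mean for each subject.
- f = 0.24 and 0.39 are borrowed from nicotine figures in section 6.1. They are not NNN/NNK extraction rates.

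**Case A: contents below quantification set to 0.** Extracted amount = 0 − 0 = 0, and ln(0) is undefined. If this applies to all pouches, no Part 3 value enters the model: 0 of 45 pairs.

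**Case B: nothing extracted, symmetric noise (f = 0).** P(difference ≤ 0) = 0.50 whatever the noise level, so about 22 of 45 Part 3 records remain. Their mean is pure noise: SE × 0.798, with SE = s × √(1/10 + 1/16) = 0.4031s. That is 0.10 of the trace content at s = 0.3 and 0.32 at s = 1.0.

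**Case C: measurable trace content that is partly extracted.** P(difference ≤ 0) = Φ(−f/SE); retained mean = f + SE × φ(f/SE)/Φ(f/SE).

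| f | s | SE | Share lost | Mean of retained |
|---|---|---|---|---|
| 0.24 | 0.3 | 0.121 | 2.4% | 0.247 |
| 0.24 | 0.6 | 0.242 | 16% | 0.310 |
| 0.24 | 1.0 | 0.403 | 28% | 0.426 |
| 0.39 | 0.3 | 0.121 | 0.1% | 0.390 |
| 0.39 | 0.6 | 0.242 | 5% | 0.418 |
| 0.39 | 1.0 | 0.403 | 17% | 0.511 |

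The first row is the favourable end: loss about 2%, almost no bias. The synopsis can be read as averaging pouches from only two days, that is 8 used pouches. Then SE = 0.3 × √(1/10 + 1/8) = 0.142 and that row's loss is 4.6%. The rows with s = 1.0 are extreme, since a normal distribution with SD equal to its mean gives about 16% of unused pouches an impossible negative content.

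**Effect on the ratio in Case B.** In a simulation of 45 subjects (Part 1 amount 1 with log-scale SD 0.5, true Part 3 amount 0, positive differences kept), the estimated geometric ratio averaged 0.005 with noise SD at 1% of the Part 1 amount and 0.027 at 5%. The true ratio is 0, so the estimate is set by the noise. Analytically, the geometric mean of the positive half is 0.530 × noise SD, that is 0.0053 and 0.0265.

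**The case against.** **The protocol does not say the pouches are free of NNN and NNK.** Section 6.1 speaks of reduced levels of toxicants. A reader might infer that the subtraction must give zero or negative values; the documents do not support that. With measurable trace content, substantial extraction and modest noise, nearly all differences are positive. This stands, and it is why the shares above are a range and not a forecast.

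**Handling of values below quantification belongs in the SAP.** It does, and its absence from the protocol is not the point. The point is that the protocol itself fixes the log-ratio model for NNN and NNK. The deferral in 17.1.1 covers missing, unused and spurious data, and a true extraction of zero is none of these. The permission to change approach after diagnostics stands in 17.8.7 and concerns the correlation models there.

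**The conclusion would hardly change.** A reader might infer that the reduction after switching would be hidden or equivalence falsely declared. The figures do not support that: ratios of 0.005 to 0.027 still show a fall of at least 97% (1 − 0.027 = 0.973), far from 0.8 to 1.25. The bias is a share of the pouch's trace content, not of Part 1 intake. Section 17.8.6 also summarizes daily exposure descriptively, and urinary NNN and NNAL are compared separately in 17.8.5. All of this stands and limits the importance.

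**The losses need not be a random half.** If one reference mean is shared by all users of a product, errors are correlated and losses cluster by product. That makes the loss less predictable but does not remove it.

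**The undefined extracted fraction is minor.** Agreed: fractions are only summarized descriptively.

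**Conclusion.** The point holds in limited form. For NNN and NNK in Part 3 the protocol prescribes a log-scale ratio model for a difference that, on its own description of the product, is likely to be at or near zero and may be zero or negative. The consequence runs from total loss of Part 3 records (contents below quantification set to 0), through about half (no extraction, symmetric noise), to about 2% or less (measurable trace content, extraction of 24% or more, per-pouch SD about 30%, 16 used pouches). Which applies cannot be determined from the documents. Where losses are material, the ratio is either not estimable or rests on positive noise and overstates Part 3 intake.

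The scope is two analytes in exploratory endpoint 6. Nicotine exposure and the primary endpoint are not affected. This should be corrected because the method is badly fixed and cheap to change, not because it threatens the trial's main conclusions.

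**What to change.** Amend section 17.8.6 and carry the change into the SAP:

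- Keep the log-ratio model and the 0.8 to 1.25 rule for daily nicotine exposure only.
- For NNN and NNK, analyse the paired Part 3 minus Part 1 difference in daily exposure on the original scale. Retain all subjects and any zero or negative values. Report a bootstrap or t interval as an estimate, without the equivalence rule.
- State how pouch contents below quantification are handled, and reconcile this with the no-imputation statement in 17.1.1. If they are set to 0 throughout, the difference reduces to minus the Part 1 intake, and the report should say so.
- Report the extracted fraction as not calculable where the unused pouch is below quantification.

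Rank-based or censored-data methods would also be defensible; what matters is to fix one before database lock. The cost is wording and one replacement analysis, with no new data. The downside is that the NNN/NNK result becomes a difference and not a ratio.
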